**Diarrhea workup**

Perform appropriate tests ([Fine and Schiller 1999](#)).

**Spot stool analysis**

- Collect stool separating it from urine (special containers, analysis immediately, exceptionally freeze samples)
- Blood

- Fecal leukocytes (Wright's staining and microscopy) or
- Clostridium difficile toxin
- Fecal cultures including Salmonella spp., Campylobacter spp., Giardia, Entamoeba, Cryptosporidium (which can lead to opportunistic infections in immunosuppressed patients), plus Shigella and pathogenic E. coli - enterotoxigenic, enterohemorrhagic etc., possibly Aeromonas, Pleisiomonas (if suspected exposure to contaminated water)

### Endoscopic examinations

Endoscopic examinations may be considered **only if absolutely necessary**. The bowel is likely to be fragile with evidence of colitis and thus great care and caution must be exercised in undertaking these invasive procedures.

- Gastroscopy to obtain jejunal fluid - re. bacterial overgrowth for cultures and biopsy of proximal jejunum to assess extent of inflammatory jejunitis
- Sigmoidoscopy - reassessment of colitis

### 12.2 Appendix 2 Guidance for hyperglycemia management

Hyperglycemia is known to be associated with the treatment with SST analogs. Clinical studies of pasireotide in healthy volunteers and in patients with Cushing's disease, acromegaly or carcinoid syndrome have reported transient, asymptomatic increases in fasting and postprandial glucose levels. Novartis has conducted 2 clinical studies ([SOM230B2216] and [SOM230B2124]) to further understand the mechanism of pasireotide-induced hyperglycemia and to evaluate the clinical utility of anti-diabetes agents in the management of pasireotide-induced hyperglycemia. Preliminary results suggest that pasireotide induces insulin suppression, particularly in the postprandial period, as being the key mechanistic driver of hyperglycemia. Based on the mechanisms of pasireotide-induced hyperglycemia and findings from the [SOM230B2124] study, appropriate management for the pasireotide-induced hyperglycemia includes the use of oral anti-diabetic agents for mild to moderate hyperglycemia, such as incretin enhancers (e.g. GLP-1analogs or DPP4 inhibitors or insulin secretagogues). Metformin is not recommended. Insulin should be used for moderate to severe hyperglycemia. Clinical monitoring and self-monitoring of blood glucose level

#### Finger -stick measurements:

[figure not shown]
**Fasting assessment:** Patients will have these checked during follow up assessments.

The glucose values from the will be recorded and sent to Mayo Clinic. At screening all patients should be informed of the signs/symptoms of hyperglycemia and educated on how to complete the patient glucose diary. The glucose values do not need to be entered into the database and should only be kept as source documentation.

The below algorithm has been created as a general guidance tool on the management of pasireotide-induced hyperglycemia during this study. The choice of therapeutic agent is primarily at the discretion of the treating physician. It is encouraged to follow the established guidelines from the ADA/EASD for the management of diabetes and consider a consultation with a diabetes expert as needed anytime during the study.

### Postprandial Plasma Glucose Criteria

The patient should be instructed on the steps to take in the event a glucose value is elevated. The below criteria is recommended:

[figure not shown]

\* Value confirmed on 2 separate occasions during the observation period.

[figure not shown]
### Fasting Plasma Glucose Criteria

The patient should be instructed on the steps to take in the event a glucose value is elevated.

\* Value confirmed on 2 separate occasions during the observation period.

**Fasting plasma glucose or postprandial plasma glucose > 250 mg/dL ( $\geq$  CTCAE grade 3)****12.3 Appendix 3 Guideline for the treatment of QT prolongation****QT-related cardiology consultation/Holter monitoring**

If at any visit a QTcF > 500msec is observed, triplicate ECGs, each 2-3 minutes apart, need to be taken approximately 1 hour after the initial ECG. The mean QTcF from the triplicate ECGs will be determined. If the mean QTcF is > 500msec, the patient has to interrupt (SQ treatment)/postpone (LAR treatment) study treatment until a cardiologist has re-evaluated the ECG (this will be done by the central cardiologist). The re-evaluation needs to be done as soon as practical but within 7 days of the initial abnormal ECG. If the cardiologist confirms a mean QTcF > 500msec, the patient has to discontinue. Otherwise and if the cardiologist confirms that at least one ECG shows a QTcF > 480msec, the cardiac assessments described for a confirmed QTcF > 480msec need to be followed.

If at any visit a  $480\text{msec} < \text{QTcF}/\text{mean QTcF} \leq 500\text{msec}$  is observed, the following steps need to be taken:

A cardiology consultation must be sought as soon as practical but within 7 days of the initial abnormal ECG and the cardiologist must re-evaluate the ECG (this can be done by the central cardiologist if the trial has one).

If a  $\text{QTcF} > 480\text{msec}$  is NOT confirmed, no further action needs to be taken.

If a  $\text{QTcF} > 480\text{msec}$  is confirmed, a cardiologist must perform a thorough examination (such as reviewing baseline ECG, concurrent medications and performing a cardiovascular examination, including at least a cardiac auscultation) to assess the patient for cardiovascular risk factors.

- If based upon the assessment by the cardiologist, the investigator considers that there is an acute cardiovascular safety risk and that the patient should not continue with study medication, the patient needs to be discontinued immediately (discontinuation criteria to be followed).
- If following the examination by the cardiologist, the investigator considers that there is not an acute cardiovascular safety risk and that the patient could continue to receive study medication, a Holter ECG (24hr or 48hr depending on the study) must be recorded soon as practical but within 7 days after the initial abnormal ECG / at the next pasireotide/octreotide LAR injection (for studies using LAR). The Holter-ECG must be started 30min prior to an injection of study medication.

The results of the ECGs, cardiac examination, Holter-ECGs and the recommendation by the cardiologist must be evaluated by the investigator to determine whether the patient should continue in the trial or not (discontinuation criteria to be followed).

#### **QT-related discontinuation criteria**

- Confirmed  $\text{QTcF} > 480\text{msec}$  and discontinuation recommended by a cardiologist
- Mean  $\text{QTcF} > 500\text{ msec}$  measured by triplicate ECGs
- Significant arrhythmia findings from Holter monitoring such as:
  1. Any ventricular or supra-ventricular tachyarrhythmia associated with symptoms of hemodynamic compromise
  2. Sustained ventricular tachycardia (>30 sec) irrespective of symptoms
  3. Recurrent non-sustained VT ( $\geq 3$  beats) during any 24-hour monitoring period
  4. Torsades de Pointes (TdP)
  5. Cardiac arrest
  6. Pause >5 seconds
  7. Second or third degree AV block
- New occurrence of clinically significant/symptomatic bradycardia
- Increased risk of QT prolongation by use of QT prolonging medication
- Hypokalemia (<3.5 mmol/L) or hypomagnesaemia (<0.7 mmol/L) confirmed by repeat testing that is either a new finding or accompanied by vomiting or diarrhea and not corrected by treatment

[figure not shown]

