**Pancreatic****Pancreatitis**

Grade 1	Maintain dose level
---------	---------------------

Grade 2	Maintain dose level
Grade 3	Omit dose and discontinue patient from study treatment
Grade 4	Omit dose and discontinue patient from study treatment
Amylase and/or lipase	
Grade 1 (> ULN - 1.5 x ULN)	Maintain dose level
Grade 2 (> 1.5 - 2.0 x ULN)	Maintain dose level
Grade 3 (> 2.0 - 5.0 x ULN)	For asymptomatic: Omit dose until resolved to ≤ Grade 1, then 
 
• If resolved ≤ 7 days, then maintain dose level
 
• If resolved > 7 days, then ↓ 1 dose level
 
 For symptomatic: Omit dose and discontinue patient from study treatment
Grade 4 (> 5.0 x ULN)	Omit dose and discontinue patient from study treatment A CT scan or other imaging study to assess the pancreas, liver and gallbladder must be performed within 1 week of the first occurrence of any ≥ CTCAE grade 3 of amylase and/or lipase.
Endocrine/metabolic	
Fasting plasma glucose (FPG) or 2-hour postprandial capillary glucose (PPG)	
FPG <126 mg/dL or PPG < 140 mg/dL	Maintain dose level
Grade 1 (> ULN – 160 mg/dL)	appendix 2 section 12.2.
Grade 2 (> 160 – 250 mg/dL)	appendix 2 section 12.2.
Grade 3 (> 250 – 500 mg/dL)	appendix 2 section 12.2.
Grade 4 (> 500 mg/dL)	appendix 2 section 12.2.
Cardiac	
Cardiac - prolonged QTc interval	

 
• QTcF > 480 ms and ≤ 500 ms
 
• QTcF > 500 msec
 
	
If at any time a QTcF > 480 ms and ≤ 500 ms is observed a cardiology consultation must be sought to re-evaluate the abnormal ECG finding.
 
 
1. Triplicate ECGs (2-3 minutes apart) need to be taken approximately 1 hour after the initial ECG.
 
2. If the mean QTcF is > 500 ms, the patient must postpone study treatment until a cardiologist has re-evaluated the ECG.
 
3. The re-evaluation of ECG needs to be done as soon as practical but within 7 days of the initial abnormal ECG.
 
4. If the cardiologist confirms a mean QTcF > 500 ms, the patient must be discontinued.
 

Cardiac general	
Grade 1 or 2	Maintain dose level
Grade 3	Omit dose until resolved to ≤ Grade 1, then ↓ 1 dose level
Grade 4	Omit dose and discontinue patient from study treatment
Other adverse events	
Grade 1 or 2	Maintain dose level
Grade 3	Omit dose until resolved to ≤ Grade 1, then ↓ 1 dose level

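### Appendix 3 lists a triplicate mean QTcF above 500 ms as a reason to discontinue with no confirmation step, while its own procedure and Table 7 discontinue once a cardiologist confirms it, so an unconfirmed mean has two possible outcomes.

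*Combined protocol and SAP*

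**What the plan says.** Four places deal with a QTcF above 500 ms.

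- **Appendix 3, procedure (QT-related cardiology consultation/Holter monitoring).** A reading above 500 ms leads to triplicate ECGs. If their mean exceeds 500 ms, the patient postpones LAR "study treatment until a cardiologist has re-evaluated the ECG (this will be done by the central cardiologist"). Then: "If the cardiologist confirms a mean QTcF > 500msec, the patient has to discontinue". The next sentence covers the alternative: "Otherwise and if the cardiologist confirms that at least one ECG shows a QTcF > 480msec", the assessments for a confirmed value above 480 ms apply. Under those, a patient judged not to be at acute cardiovascular risk can stay on study drug, with a Holter recording.
- **Appendix 3, QT-related discontinuation criteria.** One bullet is a mean QTcF above 500 ms "measured by triplicate ECGs", with nothing further. The bullet above it, for values above 480 ms, opens with the word *confirmed* and adds "and discontinuation recommended by a cardiologist".
- **Table 7 (section 6.6), prolonged QTc interval.** If the triplicate mean is above 500 ms, "the patient must postpone study treatment until a cardiologist has re-evaluated the ECG". Step 4 makes discontinuation mandatory if the cardiologist confirms a mean above 500 ms.
- **Section 6.8.** Any confirmed QTcF above 500 ms requires discontinuation. The section does not say whether the triplicates or the cardiologist supply the confirmation.

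**The concern.** A stopping rule should give the same answer wherever it is looked up. Here, an investigator who works from the bullet list stops a patient as soon as the triplicate mean exceeds 500 ms. One who works from the procedure holds the dose, waits for the cardiologist, and may resume treatment if the mean is not confirmed. Both are following the protocol, and a monitor could record either as a deviation. QT prolongation is a prominent risk in this protocol: section 1.5.1 reports a QTcF effect in healthy volunteers, section 5.2.2 has a block of QT exclusions, and ECGs are repeated throughout follow-up. The cardiologist's re-evaluation has a purpose only if it can differ from the triplicate mean, and that is the situation in which the rules part.

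**Working it through.** No arithmetic settles this point. The check is to follow one patient, with a triplicate mean above 500 ms, through each source under the two possible results of the re-evaluation.

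| Source | Cardiologist confirms mean > 500 ms | Cardiologist does not confirm it |
|---|---|---|
| Appendix 3, criteria list | Discontinue | Discontinue, read literally |
| Appendix 3, procedure | Discontinue | If at least one ECG > 480 ms is confirmed: > 480 ms assessments, treatment may continue. If none is, that sentence names no action |
| Table 7, step 4 | Discontinue | Not addressed |
| Section 6.8 | Discontinue | Depends on the meaning of *confirmed* |

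1. In the confirmed column all four agree, so there is no conflict.
2. In the unconfirmed column the two parts of Appendix 3 give different answers.
3. Section 6.8 does not break the tie. If *confirmed* means confirmed by the triplicates, it sides with the list. If it means confirmed by the cardiologist, it sides with the procedure and with Table 7.
4. The cross-reference makes the conflict circular. The > 480 ms assessments end by sending the investigator back to the discontinuation criteria. A patient who arrived there because the mean was not confirmed already meets the > 500 ms bullet, so the list cancels the branch that the procedure created.
5. The list states confirmation elsewhere: the > 480 ms bullet requires it, and the hypokalemia and hypomagnesemia bullet requires repeat testing. The > 500 ms bullet has neither.

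On frequency, the documents give no rate of disagreement between a triplicate mean and a cardiologist's re-evaluation. Two figures are only indicative. Entry excludes QTcF above 470 ms (section 5.2.2), and the reported peak effect versus placebo is 17.5 ms at 1950 µg SQ b.i.d. (section 1.5.1). A patient at the entry limit with that average effect would be at 470 + 17.5 = 487.5 ms, below 500 ms. That figure is a group result for another formulation and regimen, and individuals will vary around it. It suggests that the case is uncommon among 48 patients but does not estimate how often it occurs.

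**The case against.** The best defence is that the bullet is shorthand. In Appendix 3, triplicates arise only inside the procedure, which goes on to postponement, re-evaluation within 7 days and discontinuation if confirmed. The list closes the same appendix and may simply name that endpoint. It does not say that confirmation is unnecessary, nor whose reading supplies the mean. If the mean meant is the one the cardiologist has re-evaluated, there is no conflict. Table 7 and, arguably, section 6.8 point the same way.

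This reading is possible, but nothing in the document states it. The neighbouring bullets spell out confirmation where it is wanted, and the > 480 ms assessments refer back to the list as if it applied as written. A figure follows the list but is not visible in the text available, so it cannot be relied on by either side.

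The objection that the consequence is narrow does stand. The conflict arises only when the mean is not confirmed, and both the procedure and Table 7 hold dosing until the cardiologist has looked.

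**Conclusion.** The inconsistency is real and limited. For a triplicate mean above 500 ms that the cardiologist does not confirm, the Appendix 3 list read literally discontinues the patient, while the Appendix 3 procedure can lead to continued treatment if at least one ECG above 480 ms is confirmed. The conclusion rests on taking the bullet as printed. The number of patients affected cannot be estimated and is probably small. No endpoint, analysis or power figure changes. It should still be corrected, because a mandatory safety stop needs one reading.

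Three stronger readings are tempting and are not supported:

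- A reader might infer that Table 7 triggers the triplicates at 480 to 500 ms, against Appendix 3, because the sentence just before "Triplicate ECGs (2-3 minutes apart) need to be taken approximately 1 hour after the initial ECG" concerns that range. The left-hand cell also lists QTcF above 500 ms, and the numbered steps may belong to that entry. The row layout was lost when the table was read from PDF, so no mismatch can be claimed.
- A reader might infer that Table 7 itself lets an unconfirmed patient continue. It says nothing on that case; only the Appendix 3 procedure does, and on a condition.
- A reader might infer that a patient could be re-dosed without review. Neither the procedure nor Table 7 allows that.

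**What to change.** Reconcile the Appendix 3 procedure, the Appendix 3 discontinuation list, Table 7 step 4 and section 6.8. State the criterion once, saying whether it is the triplicate mean itself or the mean after the cardiologist's re-evaluation, and have the other places refer to it. Define *confirmed* in section 6.8 by saying who or what confirms. State in Table 7 what follows when the mean is not confirmed, and in Appendix 3 what follows when no ECG above 480 ms is confirmed either. The clinical team decides which rule applies; this review takes no position on it. The cost is a wording amendment, with no effect on sample size, visits or analysis.

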## 5.2 Inclusion/exclusion criteria

The investigator or her designee must ensure that all patients who are offered enrollment in the study meet all of the following inclusion and exclusion criteria:

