### 5.2.2 Exclusion criteria

Patients will be considered ineligible for this study if they meet any of the following criteria:

Patients with a known hypersensitivity to SST analogs or any component of the pasireotide LAR or SQ formulations.

Patients with known malabsorption syndrome, short bowel or chologenic diarrhea not controlled by specific therapeutic means.

Patients with abnormal coagulation (PT or a PTT elevated by 30% above normal limits).

Patients on continuous anticoagulation therapy. Patients who were on anticoagulant therapy must complete a washout period of at least 10 days and have confirmed normal coagulation parameters before study inclusion.

Patients with symptomatic cholelithiasis.

Patients who are not biochemically euthyroid.

Patients with known history of hypothyroidism are eligible if they are on adequate and stable replacement thyroid hormone therapy for at least 3 months.

Serum magnesium  $\geq$  ULN

QT-related exclusion criteria:

QTcF at screening  $>$  470 msec

Patients with a history of syncope or family history of idiopathic sudden death

Patients who have sustained or clinically significant cardiac arrhythmias

Risk factors for Torsades de Pointes such as hypokalemia, hypomagnesemia, cardiac failure, clinically significant/symptomatic bradycardia, or high-grade AV block

Patients with concomitant disease(s) that could prolong QT such as autonomic neuropathy (caused by diabetes, or Parkinson's disease), HIV, cirrhosis, uncontrolled hypothyroidism or cardiac failure

Family history of long QT syndrome

Concomitant medications known to prolong the QT interval.

Potassium  $<$  or  $=$  to 3.5

Patients who have any severe and/or uncontrolled medical conditions or other conditions that could affect their participation in the study such as:

Patients who have Uncontrolled diabetes as defined by HbA1c $>$ 8%\* despite adequate therapy

Patients with the presence of active or suspected acute or chronic uncontrolled infection or with a history of immunodeficiency, including a positive HIV test result (ELISA and Western blot). An HIV test will not be required; however, previous medical history will be reviewed.

Non-malignant medical illnesses that are uncontrolled or whose control may be jeopardized by the treatment with this study treatment.

Liver disease such as cirrhosis, decompensated liver disease, chronic active hepatitis or chronic persistent hepatitis.

Baseline ALT or AST  $>$ 3x ULN

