**Table 8 Visit/Study Procedure Schedule**

Test / Procedure	S	R	Days after 1 st injection					Months after initial visit											Mos. after end					
			22/2	29	50	57	85	6	9	12 	15	18	21	24	27	30	33	36 / Early Term	1	3				
Consent	X																							
History/physical	X							X		X		X		X		X		X		X				
Height,  Weight	X							X		X				X		X		X		X				
ECG 	X	X	X		X		X	X	X	X	X	X	X	X	X	X	X	X	X	X	X	X	X	
Heme Group 	X							X	X	X	X	X	X	X	X	X	X	X	X	X	X	X	X	
PT APTT	X							X		X					X							X		
Metabolic panel  eGfr 	X		X	X	X	X	X	X	X	X	X				X							X		
Hemoglobin A1C 	X						X	X	X	X	X	X	X	X	X	X	X	X	X	X	X	X	X	X
Thyroid cascade 	X							X		X	X	X			X			X			X			
MRI (CT) Scan	X									X												X		
Genotyping	X																							
Cyclosporin level 	X				X			X	X	X	X	X			X							X		
Microalbumin	X									X					X							X		
Fasting glucose 	X	X	X		X		X	X	X	X	X	X	X	X	X	X	X	X	X	X	X	X	X	X
Pregnancy Test 	X									X														
QOL SF-36v2TM	X							X		X				X			X		X		X			
SOM230/Placebo 		X	X		X	X	X	X	X	X	X	X	X	X	X	X	X	X	X	X	X	X	X	X
Concomitant meds	X	→	X	X	X	X	X	X	X	X	X	X	X	X	X	X	X	X	X	X	X	X	X	X
Gallstone (6 mo) 								X					X		X			X						
PK Bloods	X			X			X	X		X														

S= Screening

R = Randomization

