 Height required only at pre-study 12 lead ECG & interpretation at screening and ½ hour after first injection. Repeat ECG on 21st day after injection for the first 3 months then every third month. All ECGs are faxed to the Mayo Clinic ECG Core lab. Includes WBC with differential Comprehensive fasting metabolic panel includes: albumin, total bilirubin, calcium, CO2, (bicarbonate) chloride, creatinine, BUN, potassium, total protein, sodium, AST, ALT, ALP,, and glucose. Liver function tests are assessed at baseline (if baseline LFTs are **done within 7 days of day 1 of treatment** they do not have to be repeated on day 1), day 22 after first injection, day 29, day 50, 57 and 85. After day 85 and the 4th LAR Injection, monitoring should follow the existing protocol schedule. Day 22 & 50 LFTs must be available & assessed prior to dosing on days 29 (2nd injection) and 57 (3rd injection). Only in patients with associated PKD. Hemoglobin A1C is done at baseline and 3 monthly Thyroid function is also acceptable if checked within 30 days of the screening visit Bi-weekly cyclosporin levels will be monitored for the first month in enrolled patients who are on this medication (mail in test) Plasma glucose is required 6 hours after first injection. Monitor FPG or finger stick at baseline and at 21st day of treatment for first 3 months. Monitor FPG or finger stick monthly (or as clinically appropriate), thereafter.

-  Women of childbearing potential only (urine pregnancy test). If CT scan is needed, a negative pregnancy result will need to be obtained prior to performing the CT. For women of child bearing potential who will be having an MRI – a pregnancy test is not required at month 12.
-  SOM230/placebo IM injections will be given every 28 days, +/- 2 days.
-  No gallstone assessment is needed on visits where MRI is performed, as gallstones will be detected on MRI if present.
-  In year 2, safety assessments for patients crossing over from placebo to SOM 230 will be required. These will be per the same schedule after the first SOM230 injection as was performed in year 1 for all patients enrolled.

At a minimum the following safety evaluations (Table 9) are to be included in all protocols.

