## **7.5 Safety**

Safety assessments will consist of monitoring and recording all adverse events, including serious adverse events, the regular monitoring of hematology (including glycosylated hemoglobin and coagulation parameters), blood chemistry (including fasting glucose, thyroid function tests), urine for microalbumin, regular monitoring of vital signs, gallbladder by MRI/CT ultrasound, will be recorded from study enrollment until study completion.

Patients with diabetes are to be instructed to check blood glucose levels via a fingerstick several times daily, particularly for the first few days of treatment.

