### **7.5.4 Laboratory evaluations**

Patients are to fast overnight for 8 hours prior to all biochemistry samples being taken. Blood samples are to be taken in the morning. Water is allowed during this time. Laboratory samples will be analyzed locally at Mayo Clinic. Albumin, alkaline phosphatase, total bilirubin, calcium, chloride, creatinine with calculated eGFR,  $\gamma$ -GT, fasting blood glucose, potassium, total protein, AST, ALT, sodium, urea/BUN. If the total bilirubin concentration is increased above 1.5 times the upper normal limit (UNL), total bilirubin should be differentiated into the direct and indirect reacting bilirubin.

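### Appendix 3 lists confirmed low magnesium as a QT-related reason to stop study drug, but no available text schedules a magnesium test after the first injection.

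*Combined protocol and SAP*

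**What the plan says.** Appendix 3 (section 12.3) ends with a list of QT-related discontinuation criteria. One item reads "Hypokalemia (<3.5 mmol/L) or hypomagnesaemia (<0.7 mmol/L) confirmed by repeat testing that is either a new finding or accompanied by vomiting or diarrhea" and goes on to require that the abnormality was not corrected by treatment.

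Magnesium also appears in the entry criteria. Section 5.2.2 excludes patients with "Risk factors for Torsades de Pointes such as hypokalemia, hypomagnesemia, cardiac failure" and other conditions. A separate line headed "Serum magnesium" excludes values at or above the upper limit of normal. Section 5.2 says the investigator or designee "must ensure that all patients who are offered enrollment in the study meet all of the following inclusion and exclusion criteria".

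The monitoring sections do not mention it. The Table 8 row "Metabolic panel" is defined in footnote 4, whose list includes "creatinine, BUN, potassium, total protein, sodium, AST, ALT, ALP" and glucose. Section 7.5.4 gives a similar list, ending "fasting blood glucose, potassium, total protein, AST, ALT, sodium, urea/BUN". Section 7.5 refers to "blood chemistry (including fasting glucose, thyroid function tests" without naming an electrolyte. Table 9 covers ECG, gallstones, glucose, thyroid function and HbA1c.

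**The concern.** The Appendix 3 item needs a low value on treatment, a repeat that confirms it and, for the new-finding limb, an earlier value for comparison. The plan schedules the potassium measurements that this requires. For magnesium, a site that followed the schedule exactly would have no result after the first injection, so half of a paired safety rule would have nothing routine to act on.

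The setting is foreseeable. The rule itself links low magnesium to vomiting and diarrhea. Section 1.5 reports diarrhea in most healthy volunteers given the LAR formulation, in 12 of 35 patients with acromegaly and, adding 4/12, 4/14 and 4/16, in 12 of 42 patients with carcinoid tumors. Section 5.2.2 names hypomagnesemia as a Torsades risk factor. What is at stake is whether a criterion the protocol states can be applied dependably.

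**Working it through.** **Places compared**

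| Place | Potassium | Magnesium |
|---|---|---|
| Section 5.2.2, entry | excluded in words and at or below 3.5 | excluded in words if low; at or above ULN numerically |
| Appendix 3, QT criteria | below 3.5 mmol/L | below 0.7 mmol/L |
| Table 8 footnote 4 panel | named | not named |
| Section 7.5.4 list | named | not named |
| Table 9 | not named | not named |
| Section 7.5 | not named | not named |
| Section 6.8 and Table 7 QTc row | not named | not named |

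The two electrolytes share one stopping item, but only one of them is in the laboratory lists.

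**Panel count, from the Table 8 metabolic panel row**

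- Marks: 1 at screening + 5 (days 22, 29, 50, 57, 85) + 3 (months 6, 9, 12) + 1 (month 15) + 2 later = 12.
- After the first injection: 12 − 1 = 11. Potassium is named for 11 of 11, magnesium for 0 of 11.
- The months of the last two marks are uncertain because the table's columns are broken. The total of 11 does not depend on them.
- Section 4 lists 15 time points for blood and urine tests (5 days and 10 months) but names no analyte, so it does not fill the gap.

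**Across the trial (48 patients, 16 on placebo; sections 4.1 and 6.2)**

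- Base schedule after the first injection: 11 × 48 = 528 panels at most.
- Under Table 8 footnote 13, placebo patients who cross over repeat the five early panels in year 2. Day 85 after crossover falls near month 15 (85 / 30.4 = 2.8 months after month 12), where Table 8 already has a panel. Counting that panel once adds 4 × 16 = 64, giving 528 + 64 = 592. If it were drawn separately the addition would be 5 × 16 = 80, giving 608.
- Magnesium is named for none of them. These totals describe the schedule and do not estimate harm.

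**Entry.** Section 5.2 requires every criterion to be met and section 5.2.2 has two magnesium-related exclusions, so a screening value is implied even though Table 8 does not name it. The gap is therefore mainly in the on-treatment values.

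**The case against.** **Standing of the rule.** The strongest reply is that this is guidance and not one of the trial's mandatory stops. Section 6.8 holds the circumstances that require discontinuation; its QT item concerns QTcF and names no electrolyte, and neither does the QTc row of Table 7. Table 7 refers to the appendices as guidance, and Appendix 3 carries wording meant for several studies, including subcutaneous treatment. This stands: the rule rests on the appendix alone. It remains part of this protocol, with a numeric trigger, and the appendix text tells the investigator to follow its discontinuation criteria.

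**Event-triggered reading.** Appendix 3 starts from an abnormal QTcF, and its Holter findings likewise arise only after a QTcF above 480 msec is confirmed. Appendix 1 provides for further testing when severe diarrhea persists. So the magnesium item could be meant to apply only within such a work-up. This partly stands, and the documents do not settle it. Neither work-up names magnesium, however: the cardiology examination gives other examples, and the diarrhea work-up lists stool tests and endoscopy. Even on this reading the plan does not ask for the value it relies on.

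**Incomplete lists.** The panel lists also omit amylase and lipase, although Table 7 sets on-treatment thresholds for both, and Table 8 omits the hepatitis B and C tests needed at entry. Absence from a list therefore does not prove that a test is not done. This stands, and it limits the conclusion to what is scheduled in writing.

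**Other safeguards.** Scheduled ECGs, cardiology review, the ban on QT-prolonging drugs and potassium monitoring all reduce risk. None supplies a magnesium value. The section 6.8 stop for clinically significant grade 3 or higher chemistry abnormalities also needs the analyte to be measured.

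**Conclusion.** The point holds in a limited form. Appendix 3 sets a magnesium criterion, no available text schedules a magnesium test after the first injection, and that half of the rule can act only on unscheduled results. In numbers, magnesium is named for 0 of 11 panels per patient and potassium for 11 of 11. The rule and the schedule do not match, and the repair is cheap. Power and the primary analysis are unaffected.

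A reader might infer more, and the documents do not support it:

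- That the rule cannot operate at all. Unscheduled testing remains possible, so it can operate, though not reliably.
- That patients enter without a magnesium check. The entry criteria imply one.
- That the exclusion at or above ULN is a sign error. The trial admits patients with eGFR just above 30, so an upper limit may be deliberate; only the sponsor can say.
- That patients face a known excess QT risk. The QTcF effect in section 1.5.1 was seen at 1950 µg subcutaneously twice daily, not with LAR 60 mg, and the documents give no frequency of low magnesium.

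The conclusion assumes that footnote 4 and section 7.5.4 define what sites are asked to measure. It also assumes that the lack of correction by treatment applies to both limbs of the criterion; the grammar would allow it to apply only to the vomiting or diarrhea limb, and the finding is the same either way. The figure beside the criteria list and a short stretch of section 1.5.2.1 are not available, so the statement covers the visible text only.

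**What to change.** 1. Add serum magnesium to the metabolic panel in Table 8 footnote 4 and to the list in section 7.5.4, at screening and at each later panel, on blood already drawn.
2. In Appendices 1 and 3, require potassium and magnesium whenever QTcF exceeds 480 msec or significant vomiting or diarrhea occurs. This makes the rule workable under either reading.
3. Optionally, give the entry exclusion for hypomagnesemia a number that matches Appendix 3: below 0.7 mmol/L, or 0.7 × 24.305 / 10 = 1.70 mg/dL. Leave the exclusion at or above ULN as it is unless the sponsor confirms an error.

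**Cost.** One added analyte on up to 12 samples per patient: 12 × 48 = 576 tests. Crossover repeats add 64 if the year-2 day 85 panel coincides with month 15 (576 + 64 = 640), or 80 if it does not (656). The scheduled tests need no extra blood draw; the event-triggered ones add some unscheduled samples, whose number the documents do not allow one to estimate. Adding a safety test calls for a short amendment with IRB approval (section 9, item 4).
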